## 4.2 Duration of Study

The duration of the study is defined for each patient as the date signed written informed consent is provided through the posttreatment visit (visit 7) on day 126.

### **4.2.1 Withdrawal of Patients from the Study**

All patients have the right to withdraw from the study at any time, for any reason, without prejudice. At any point, the investigator may discontinue the patient's study participation at his/her discretion and ensure the patient receives appropriate medical care; the investigator may also consult the medical monitor to discuss out-of-range test results. The patient may also be withdrawn or terminated at the request of the sponsor. Additionally, although Allergan has every intention of completing the study, Allergan reserves the right to discontinue the study at any time for clinical or administrative reasons.

As part of the clinical laboratory assessments, liver enzymes (ALT, AST, alkaline phosphatase), and total bilirubin values will be evaluated for all patients. In the event that a patient's bilirubin level is elevated after the first dose of study drug, a fractionated bilirubin test should be performed if possible. In general, an increase in serum aminotransferases to greater than 3 times ULN after the first dose in patients who entered the study with normal baseline values should be followed by repeat testing within 48 to 72 hours of all 4 of the usual serum measures (ALT, AST, alkaline phosphatase, and total bilirubin) to confirm the abnormalities and to determine if they are increasing or decreasing. There also should be an inquiry made about symptoms. Patients should be observed for other possible causes of elevated liver function test results including acute viral hepatitis, alcoholic and autoimmune hepatitis, hepatobiliary disorders, nonalcoholic steatohepatitis, cardiovascular causes, or concomitant treatments. If baseline transaminases are found to be elevated above the ULN, the preceding guidance should be considered in patients who double their baseline value(s). If the repeat value for ALT or total bilirubin is unchanged or indicates decreasing activity, monitoring should continue at weekly intervals until the results are acceptable or normalized. If any value has increased further, immediate close observation is required. If close monitoring is not possible, the drug should be discontinued.

Withdrawal from the study should be considered if any of the following occurs:

- ALT or AST  $>8 \times$  the ULN
- ALT or AST  $>5 \times$  ULN for more than 2 weeks
- ALT or AST  $>3 \times$  ULN and (total bilirubin  $>2 \times$  ULN or international normalized ratio  $>1.5$ )

- ALT or AST  $>3 \times$  ULN with the appearance of fatigue, nausea, vomiting, right upper quadrant pain or tenderness, fever, rash, and/or eosinophilia ( $>5\%$ )

For complete information regarding withdrawal from the study in the event of a marked elevation of liver enzymes, refer to Pages 9-10 of Guidance for Industry – Drug-Induced Liver Injury: Premarketing Clinical Evaluation ([US Department of health and Human Services 2009](#)).

#### **4.2.2 Handling of Withdrawals**

Patients who discontinue study treatment or active participation in the study will no longer receive study drug.

When a patient withdraws from the study, the reason(s) for withdrawal shall be recorded by the investigator on the relevant page of the electronic case report form (eCRF). Whenever possible, for all patients who discontinue study treatment or withdraw from the study prematurely will undergo all end-of-treatment/early withdrawal visit assessments. Patients who fail to return for final assessments will be contacted by the site in an attempt to have them comply with the protocol. For patients that are considered to be lost to follow-up, the site should make every attempt possible to contact the patient (e.g., via documented phone call attempts and if necessary, a certified letter to the patient).

It is vital to obtain follow-up data on any patient withdrawn because of an AE or serious AE (SAE). In every case, efforts must be made to undertake protocol-specified safety follow-up procedures until resolution or stabilization.

#### **4.2.3 Replacements**

Patients who discontinue participation in the study for any reason after randomization will not be replaced.

## **5 Study Treatments**

### **5.1 Method of Assigning Patients to Treatment Groups**

Approximately 340 patients will be randomly assigned (in a 1:1 ratio) to 1 of 2 treatment groups (eluxadoline 100 mg BID or matching placebo).

The randomization schedule will be sequestered until the study is unblinded after database lock. It will also use an appropriate block size, which will not be revealed to the study sites.

The randomization mechanism for the study will be deployed within an interactive response system (IxRS) and accessible 24 hours a day to authorized users. Study sites will access the IxRS to execute each randomization after a patient has met all prerequisites for randomization and has completed all scheduled procedures for day 1. Study site personnel, who are all blinded to treatment assignment, will receive a randomization notification indicating only the unique patient identifier and the date and time of randomization for each patient.

All patients will be assigned a unique patient number by the randomization system. After a patient number has been assigned, the number will not be reused even if the patient withdraws before receiving any study drug.

### **5.2 Treatments Administered**

Patients will be randomly assigned to 1 of 2 treatment groups as follows:

- Group 1: Eluxadoline 100 mg oral tablets BID with food
- Group 2: Matching placebo oral tablets BID with food

The study drug must be swallowed whole with liquid and not chewed, divided, dissolved, or crushed.

In addition, patients will receive instructions for use of loperamide rescue medication for acute treatment of uncontrolled diarrhea (refer to Section 5.9 for details).

### 5.3 Identity of Study Drug

Eluxadoline will be supplied as 100-mg, immediate release, film-coated (Opadry II) tablets. The excipients included in the formulation are microcrystalline cellulose, silicon dioxide, crospovidone, mannitol, and magnesium stearate. Placebo tablets of matching tablet image contain the same excipients. [REDACTED], on behalf of the sponsor, will provide adequate supplies of eluxadoline and matching placebo tablets of identical size and shape to study sites.

The following drug supplies will be used in the study:

Product	Supplied as:
Eluxadoline	100-mg tablets
Placebo	100-mg tablets

Patients in each treatment group will receive a bottle containing 4-weeks' worth of study drug at randomization (visit 3), week 4 (visit 4), and week 8 (visit 5). Patients will be instructed to take 1 tablet BID with food.

### 5.4 Management of Clinical Supplies

#### 5.4.1 Study Drug Packaging and Storage

The study drug will be packaged and labeled according to current Good Manufacturing Practices and local regulations.

The study drug will be packaged in child-resistant 70-count bottles by [REDACTED] on behalf of the sponsor. The bottles will be labeled with double-blinded labels.

Each bottle will contain a (randomized) dosage for 1 patient for 4 weeks of the 12-week double-blind treatment period and will be distributed at each of the scheduled visits during the treatment period: randomization (visit 3), week 4 (visit 4), and week 8 (visit 5).

Recommended storage conditions for study drug are as per the commercial product. The study drug will be stored in controlled temperatures ranging from [REDACTED]

[REDACTED]

[REDACTED] The storage conditions will be indicated on the label. Expiry dates will

be provided directly on the label or communicated to the sites with an expiry memo and/or managed electronically if drug distribution for the study is managed by IxRS.

#### **5.4.2 Test Article Accountability**

The investigator will maintain accurate records of receipt of all test articles, including dates of receipt. In addition, accurate records will be kept regarding when and how much test article is dispensed and used by each patient in the study. Reasons for departure from the expected dispensing regimen must also be recorded. At the completion of the study, to satisfy regulatory requirements regarding drug accountability, all study drugs will be reconciled and retained or destroyed according to applicable regulations.

#### **5.4.3 Other Supplies**

Patients will be provided with instructions on how to enter their diary data into the ePRO. Laboratory kits for assessments will be provided to the sites centrally.

### **5.5 Overdose Management**

An overdose is any dose of study treatment given to a patient or taken by a patient that exceeds the dose described in the protocol. Any overdose, with or without associated AEs, must be promptly reported to the medical monitor. Overdoses without signs or symptoms do not need to be recorded as AEs; in case of any AEs associated with the overdose, these should be reported on relevant AE/SAE sections in the eCRF.

#### **5.5.1 Treatment of Overdose**

No reports of overdosage with eluxadoline have been reported.

In the event of acute overdose, the stomach should be emptied and adequate hydration maintained. The patient should be carefully observed and given standard supportive treatment as required. Given eluxadoline's action at opioid receptors, administration of a narcotic mu-opioid antagonist, such as naloxone, should be considered. Considering the short half-life of naloxone, repeated administration may be necessary. In the event of naloxone administration, patients should be monitored closely for the return of overdose symptoms, which may indicate need for repeated naloxone injection ([VIBERZI PI 2015](#)).

### **5.5.2 Medication Errors**

Dispensing study treatment to be taken by patients in an outpatient study increases risk for medication errors. All errors in medication dispensing or administration must be carefully documented. These errors may include but are not limited to providing the wrong dose, losing medication, or administration at the wrong time of day. Medication adherence will be emphasized at every study visit. Additional adherence procedures and/or technology, such as a mobile device application, may be implemented.

### **5.5.3 Treatment of Medication Errors**

The treatment of medication errors should be discussed with the medical monitor on a case by case basis. In the case of overdose, refer to Section [5.5.1](#).

## **5.6 Blinding**

Patients will be randomly assigned to double-blind treatment of eluxadoline at a dose of 100 mg BID or placebo BID. Blinding of the placebo tablets and eluxadoline tablets will be maintained throughout the study by using active and placebo tablets that are identical in appearance. The randomization schedules and treatment assignments will remain sequestered until the study blind is broken.

### **5.6.1 Breaking the Blind**

When necessary for the safety and proper treatment of the patient, the investigator can unblind the patient's treatment assignment to determine which treatment has been assigned and institute appropriate follow-up care. When possible, the sponsor (Allergan Medical Safety Physician) should be notified prior to unblinding study drug. The investigator should inform the sponsor (Allergan Medical Safety Physician) of the unblinding if there is no notification prior to the unblinding.

The treatment assignment for the patient can be determined by designated site personnel in the IxRS system via password protected access. The reason for breaking the code must be recorded in the patient's source documents.

## 5.7 Treatment Compliance

Treatment compliance will be assessed at the study site by pill counts. This review will be documented in the source documents.

## 5.8 Prior and Concomitant Therapy

All prescription drugs, herbal products, vitamins, minerals, and over-the-counter medications taken within 2 weeks prior to randomization will be recorded as prior medications. All medications taken after randomization and through the early termination or follow-up visit will be recorded as concomitant therapy. Use of all concomitant medications will be recorded in the patient's eCRF. Any changes in concomitant medications will also be recorded in the patient's eCRF. The minimum requirement is that drug name and the dates of administration are to be recorded. It will also be determined which prior medications were prescribed or taken over-the-counter by patients for the treatment of IBS-D.

The following medications are prohibited before and during the study, as indicated:

- 5-HT3 antagonists (e.g., alosetron or ondansetron); prohibition begins within 14 days of screening.
- Aspirin or aspirin-containing medications (>325 mg of aspirin per day) or nonsteroidal anti-inflammatory drugs, when taken specifically for the symptoms of IBS; prohibition begins within 14 days of randomization.
- Investigational drug or investigational medical device within 30 days prior to randomization.
- Narcotics or opioid-containing agents, tramadol, docusate, enemas, or GI preparations (including antacids containing aluminum or magnesium, antidiarrheal agents [except loperamide rescue medication after randomization], antinausea agents, antispasmodic agents, bismuth, or prokinetic agents); prohibition begins within 14 days of randomization.
- Rifaximin or other antibiotics (with the exception of topical antibiotics or a 1-day course with an antibiotic); prohibition begins within 28 days of randomization (see exclusion criteria number [27](#) for details).

Stable doses of antidepressants (i.e., for the 3 months prior to screening) can be taken during the study. Additionally, medications taken for the treatment of allergies, chronic medical conditions, and migraine headaches can be taken during this study (with the exception of opioids for acute treatment of migraines). Patients must be on a stable dose of medication for chronic migraines or preventive therapy for at least 1 month at screening. As-needed use of benzodiazepines for anxiety is permitted during the study.

Any concomitant medication deemed necessary for the welfare of the patient during the study may be given at the discretion of the investigator. However, it is the responsibility of the investigator to ensure that details regarding the medication are recorded in full in the source documents as well as in the eCRF.

## **5.9 Acute Loperamide Rescue Medication for Uncontrolled Diarrhea**

Use of loperamide rescue medication for the acute treatment of uncontrolled diarrhea will not be allowed within 14 days prior to randomization.

During the double-blind Treatment period and the Posttreatment period of the study, patients will be allowed to take loperamide rescue medication for the acute treatment of uncontrolled diarrhea. Loperamide at a unit dose of 2 mg may be taken once approximately every 6 hours with the following guidelines:

- No more than 4 unit doses over a continuous 24-hour time period (8 mg/day)
- No more than 7 unit doses over a continuous 48-hour time period (14 mg over 2 days)
- No more than 11 unit doses over a continuous 7-day time period

The use of loperamide rescue medication should be recorded by the patient in the ePRO diary. If a patient uses more than the allowed amount of loperamide rescue medication the ePRO system will generate a notification to alert the investigator. Excessive use of loperamide rescue medication may be cause for study discontinuation but will not be considered a protocol violation.

## 6 Study Assessments and Procedures

[REDACTED]

[REDACTED]

[REDACTED]

[REDACTED]

[REDACTED]

[REDACTED]

[REDACTED]

[REDACTED]

[REDACTED]

[REDACTED]

[REDACTED]

[REDACTED]

[REDACTED]

[REDACTED]

[REDACTED]

[REDACTED]

[REDACTED]

[REDACTED]

[REDACTED]

[REDACTED]

[REDACTED]

[REDACTED]

[REDACTED]

[REDACTED]

[REDACTED]

[REDACTED]

[REDACTED]

[REDACTED]

[REDACTED]

[REDACTED]

[REDACTED]

[REDACTED]

[REDACTED]

[REDACTED]

[REDACTED]

[REDACTED]

[REDACTED]

[REDACTED]

[REDACTED]

[REDACTED]

[REDACTED]

[REDACTED]

[REDACTED]

[REDACTED]

[REDACTED]

[REDACTED]

[REDACTED]

[REDACTED]

[REDACTED]

[REDACTED]

[REDACTED]

[REDACTED]

[REDACTED]

[REDACTED]

[REDACTED]

[REDACTED]

[REDACTED]

[REDACTED]

[REDACTED]

[REDACTED]

[REDACTED]

[REDACTED]

[REDACTED]

[REDACTED]

## 6.2 Efficacy Assessments

### 6.2.1 Daily IBS Symptoms

Patients will be required to access the ePRO diary each evening, preferably at the same time each day, to record daily IBS symptoms:

- Stool Consistency: During their daily ePRO entry throughout the 12 weeks of double-blind treatment period, patients will be asked to rate the BSS most representative of the past 24 hours. The patient-reported BSS is a 1 to 7 scale where 1 corresponds to a hard stool and 7 corresponds to watery stool (Appendix [12.3](#)):

1=Separate hard lumps like nuts (difficult to pass)

2=Sausage shaped but lumpy

3=Like a sausage but with cracks on surface

4=Like a sausage or snake, smooth and soft

5=Soft blobs with clear-cut edges (passed easily)

6=Fluffy pieces with ragged edges, a mushy stool

7=Watery, no solid pieces (entirely liquid)

- Worst Abdominal Pain: During their daily ePRO entry throughout the 12 weeks of double-blind treatment period, patients will be asked to rate their WAP in the past 24 hours. The patient-reported WAP in the past 24 hours will be recorded on a 0 to 10 scale, where 0 corresponds to no pain and 10 corresponds to worst imaginable pain.
- Abdominal Discomfort: During their daily ePRO entry throughout the 12 weeks of double-blind treatment period, patients will be asked to rate their abdominal discomfort in the past 24 hours. The patient-reported worst abdominal discomfort in the past 24 hours will be recorded on a 0 to 10 scale, where 0 corresponds to no discomfort and 10 corresponds to worst imaginable discomfort.
- Abdominal Bloating: During their daily ePRO entry throughout the 12 weeks of double blind treatment period, patients will be asked to rate their abdominal bloating in the past 24 hours. The patient-reported worst abdominal bloating in the past 24 hours will be recorded on a 0 to 10 scale, where 0 corresponds to no bloating and 10 corresponds to worst imaginable bloating.
- Frequency, Urgency and Incontinence: During their daily ePRO entry throughout the 12 weeks of double-blind treatment period, patients will be asked to record the number of bowel movements (and characteristics, where applicable), number of urgency episodes, and number of episodes of fecal incontinence, over the past 24 hours.

[REDACTED]

[REDACTED]

[REDACTED]

[REDACTED]

[REDACTED]

[REDACTED]

[REDACTED]

[REDACTED]

[REDACTED]

[REDACTED]

[REDACTED]

[REDACTED]

[REDACTED]

[REDACTED]

[REDACTED]

[REDACTED]

[REDACTED]

[REDACTED]

[REDACTED]

[REDACTED]

[REDACTED]

[REDACTED]

[REDACTED]

[REDACTED]

[REDACTED]

[REDACTED]

[REDACTED]

[REDACTED]

[REDACTED]

[REDACTED]

[REDACTED]

[REDACTED]

[REDACTED]

[REDACTED]

[REDACTED]

[REDACTED]

[REDACTED]

[REDACTED]

[REDACTED]

### **6.3.1 Adverse Events**

Adverse events occurring during the study will be recorded in an AE eCRF. If AEs occur, the first concern will be the safety of the study participants.

#### **6.3.1.1 Definitions of Adverse Events**

An AE is any untoward medical occurrence in a patient or clinical investigation subject administered a pharmaceutical product and that does not necessarily have a causal relationship with this treatment. An AE can therefore be any unfavorable and unintended sign (including an abnormal laboratory finding), symptom, or disease temporally associated with the use of a medicinal (investigational) product, whether or not related to the medicinal (investigational) product. In addition, during the screening period, AEs will be assessed regardless of the administration of a pharmaceutical product.

Note: Adverse events must be collected once informed consent has been obtained, regardless of whether or not the patient has been administered study drug. Progression of treatment

indication including new or worsening of anticipated clinical signs or symptoms, which are collected as clinical efficacy variables and assessed as unequivocally associated with the disease progression and/or lack of efficacy, should NOT be reported as AEs unless the disease progression is greater than anticipated in the natural course of the disease.

Adverse events will be assessed, documented, and recorded in the eCRF throughout the study (i.e., after informed consent has been obtained). At each visit, after the study assessments have been completed, the investigator will begin by querying for AEs by asking each subject a general, non-directed question such as “How have you been feeling since the last visit?” Directed questioning and examination will then be done as appropriate. All reported AEs will be documented in the appropriate eCRF.

Any abnormal laboratory test results (hematology, serum chemistry, or serum lipase) or other safety assessments (e.g., vital sign measurements), including those that worsen from baseline, felt to be clinically significant in the medical and scientific judgment of the investigator are to be recorded as AEs or SAEs. See Section 4.2.1 for specific instructions for monitoring patients with abnormal liver function tests.

However, any clinically significant safety assessments that are associated with the underlying disease, unless judged by the investigator to be more severe than expected for the patient’s condition, are **not** to be reported as AEs or SAEs.

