The actual ePRO data entered by the patients will not be provided to the investigative site staff at the time of randomization or during the study to prevent any potential bias in subsequent patient entries. However, periodic notifications will be generated to inform the investigator of patients' ongoing compliance with ePRO diary entries and to alert investigators if patients have experienced episodes of constipation or have required excessive loperamide rescue medication for acute treatment of uncontrolled diarrhea.

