### **6.3.1.2 Serious Adverse Event:**

An SAE is any AE occurring at any dose that results in any of the following outcomes: death, a life-threatening AE, inpatient hospitalization or prolongation of existing hospitalization, a persistent or significant disability/incapacity, or a congenital anomaly/birth defect. Important medical events that may not result in death, be life-threatening, or require hospitalization may be considered an SAE when, based upon appropriate medical judgment, they may jeopardize the patient or subject and may require medical or surgical intervention to prevent one of the outcomes listed in this definition (See Section 6.3.1.4 for procedures for reporting an SAE).

Allergan considers all cancer AEs as SAEs. In addition, Allergan considers any abortion (spontaneous or nonspontaneous) as an SAE.

Pre-planned surgeries or procedures for pre-existing, known medical conditions for which a patient requires hospitalization is not reportable as an SAE. Any pre-planned surgery or procedure should be clearly documented in the site source documents by the medically qualified investigator at the time of the patient's entry into the study. If it has not been documented at the time of the patient's entry into the study, then it should be documented as an SAE and reported to Allergan.

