### **6.3.1.4 Reporting Serious Adverse Events**

Any SAE occurring during the study period (beginning with informed consent) and for at least 30 days after the last dose of study drug must be immediately reported but no later than 24 hours after learning of an SAE. Serious AEs must be reported directly to Allergan in the US and Canada as listed on the Allergan Study Contacts Page and recorded on the SAE form. All subjects with an SAE must be followed up and the outcomes reported. The investigator must supply the sponsor and the IRB/IEC with any additional requested information (e.g., autopsy reports and discharge summaries).

In the event of an SAE, the investigator must:

1. Notify Allergan/ [REDACTED] immediately by fax or email using the SAE form (contact details can be found on page 1 of the SAE form); phone numbers and relevant Allergan personnel contacts are also on the front page of protocol and Study Contacts Page.
2. Obtain and maintain in his/her files all pertinent medical records, information, and medical judgments from colleagues who assisted in the treatment and follow-up of the subject.

3. Provide Allergan/ [REDACTED] with a complete, written description of the AE(s) on the SAE form describing the event chronologically, including any treatment given (e.g., medications administered, procedures performed) for the AE(s). Summarize relevant clinical information about the event: signs, symptoms, diagnosis, clinical course and relevant clinical laboratory tests, etc. Include any additional or alternative explanation(s) for the causality which includes a statement as to whether the event was or was not related to the use of the investigational drug.

4. Promptly inform the governing IRB/IEC of the SAE as required by the IRB/IEC, local regulations, and the governing health authorities.

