## **6.6 Laboratory Analyses**

The contract research organization central laboratory will perform all clinical laboratory tests, except urine pregnancy tests, which will be performed locally at the study site. The details related to sample handling, blood draw amounts, tubes, shipping, address, etc. are available in a separate laboratory manual.

Blood and urine samples for hematology, serum chemistry, serum lipase, and serum and urine pregnancy tests will be prepared using standard procedures.

Hematology and serum chemistry testing will be completed at screening, baseline (day 1), week 4, and all subsequent study visits through week 14 (posttreatment follow-up visit). Serum lipase testing will be performed at screening and baseline (day 1). Unscheduled blood draws for additional serum chemistry testing (lipase specifically) should be completed when possible for any patients with confirmed or suspected AEs of pancreatitis.

In addition, pregnancy tests will be performed for all women according to local procedures unless they are surgically sterile or there is a documented history of their postmenopausal status. A serum pregnancy test will be performed at screening and urine pregnancy tests will be performed at all other study visits through week 12 (or early withdrawal study visit), unless a serum pregnancy test is preferred at the discretion of the investigator or if required by local regulations. The serum pregnancy test will be performed by the central laboratory.

The blood samples will be used for the following tests:

Hematology: white blood cell count with differential, hemoglobin, hematocrit, platelet count, red blood cell count, mean corpuscular volume, mean corpuscular hemoglobin, and mean corpuscular hemoglobin concentration.

Serum Chemistry: albumin, alkaline phosphatase, ALT, AST, blood urea nitrogen, carbon dioxide, calcium (albumin corrected), chloride, creatinine, glucose, lactate dehydrogenase, phosphorus, potassium, sodium, total bilirubin\*, and total protein. Serum lipase will be tested at screening and baseline (day 1) only. Thyroid-stimulating hormone will be tested at screening only.

\*Note: If total bilirubin values are elevated in a patient who has received at least 1 dose of study drug, fractionated levels will also be determined if possible.

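### The exceptions in Section 6.3.1.1 have no carve-out for serious events, so a hospitalised event attributed to IBS-D could be recorded as neither AE nor SAE

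*Protocol*

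**What the plan says.** Protocol Section 6.3.1.1 contains two separate exceptions to AE reporting.

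- **Symptoms.** New or worsening signs or symptoms of the treated condition that are "collected as clinical efficacy variables and assessed as unequivocally associated with the disease progression and/or lack of efficacy, should NOT be reported as AEs". The override follows at once: "unless the disease progression is greater than anticipated in the natural course of the disease". This sentence speaks of AEs only.
- **Safety assessments.** After telling sites to record clinically significant laboratory and other safety findings, the section withdraws that instruction for "any clinically significant safety assessments that are associated with the underlying disease, unless judged by the investigator to be more severe than expected". This sentence excludes such findings from both AE and SAE reporting.

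Section 6.3.1.2 defines seriousness by outcome, inpatient hospitalisation among them, but starts from the AE: "An SAE is any AE occurring at any dose that results in any of the following outcomes". The one kind of admission it exempts is a pre-planned procedure for a known condition. If that plan was not documented at entry, the admission is to be reported as an SAE.

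Section 6.3.1.4 sets the 24-hour duty, which covers "Any SAE occurring during the study period (beginning with informed consent"). The duty runs on for 30 days or more once dosing has ended.

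**The concern.** The symptoms that Section 6.2.1 collects as efficacy variables (worst abdominal pain, discomfort, bloating, stool consistency, bowel frequency, urgency, incontinence) are the ones most likely to bring a patient with IBS-D to hospital for an abdominal complaint. Neither exception says what happens when such an event meets a seriousness criterion. An outcome-based definition, which should be mechanical, becomes conditional on a prior judgment about cause and expectedness.

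Safety and tolerability against placebo is one of the two objectives in Section 2. A serious event excluded at this first step would miss the expedited report and would not enter the AE or SAE records from which the arms are compared. The protocol provides for neither a safety monitoring committee (Section 6.4) nor an external data monitoring committee (Section 10.1.1).

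**Working it through.** The plan states no figure on this point, so the check is a reading of the sections in sequence. Take a patient admitted for abdominal pain that the investigator attributes to IBS-D.

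1. **Is the symptom an efficacy variable?** Yes. Worst abdominal pain is recorded daily under Section 6.2.1, so the symptom exception in 6.3.1.1 can apply.
2. **Is the event kept out of AE reporting?** It is, if it is assessed as unequivocally due to disease or lack of efficacy and progression is not judged beyond the expected course. Both tests are judgments. Neither mentions hospitalisation or any other listed outcome.
3. **Does Section 6.3.1.2 bring it back?** Not by its wording. An SAE is an AE with a listed outcome. An event excluded at step 2 is not an AE, so the hospitalisation criterion is never reached.
4. **Does Section 6.3.1.4 bring it back?** No. The 24-hour duty attaches to SAEs, and step 3 has produced none.
5. **Does any other visible rule bring it back?** None was found. The rule on pre-planned admissions points the other way: an unplanned admission is normally reportable, which makes the silence in 6.3.1.1 an inconsistency to reconcile.

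The second exception needs no such chain. A laboratory or other safety finding that is clinically significant, associated with the underlying disease and not judged more severe than expected is excluded from SAE reporting directly, again without regard to outcome.

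**Size.** The one input from the plan is 170 patients per arm (Section 7.5). If all are dosed, one omitted event changes an arm's SAE rate by 1/170 = 0.0059, or 0.59 percentage points. The documents give neither an expected SAE rate nor the share of events that would be attributed to disease, so no expected number of lost events can be derived.

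**The case against.** The strongest reply is that the symptom exception is narrow. The attribution must be unequivocal, and the override allows reporting whenever progression exceeds what was anticipated. Section 1 describes IBS as not life threatening, so an admission is a natural candidate for that override. This stands in part: many investigators would report the admission. But the override permits reporting and does not require it, because it is not tied to seriousness.

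Several stronger readings are tempting, and the documents do not support them.

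- **Both exceptions concern symptoms.** They do not. The second qualifies the paragraph on laboratory results, vital signs and other safety assessments. Only the first reaches pain or diarrhoea. Dehydration is not an efficacy variable, so the first does not cover it.
- **Investigators cannot judge attribution because they do not see the diary.** Section 3.1 does say that "The actual ePRO data entered by the patients will not be provided to the investigative site staff". But Section 6.3.1.1 provides questioning at each visit, with directed questions and examination as appropriate, and less information makes an unequivocal attribution harder to reach.
- **Excluded pain would fail to trigger a lipase test.** Section 6.6 asks for unscheduled testing "for any patients with confirmed or suspected AEs of pancreatitis". Pain that raises that suspicion is not unequivocally IBS-D.
- **Events that stop treatment disappear.** Withdrawal reasons go on the eCRF (Section 4.2.2) and are tabulated with a p-value (SAP Section 3.2).

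Redaction also limits the point. Text just before Section 6.3.1, text after Section 6.3.2.2, and the synopsis entry on safety assessments are blacked out, and the SAP safety section is not visible. A rule on serious events could be there.

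**Conclusion.** The point holds for the visible text. Sections 6.3.1.1, 6.3.1.2 and 6.3.1.4 do not agree on whether an event meeting a seriousness criterion is reported when it is attributed to IBS-D, and read literally they allow it to be left out. This is a stated exclusion rule, not missing detail.

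It should not be taken to mean that such events are unreportable or will be lost; the omission depends on discretion. Nor can a distortion of the treatment comparison be quantified. The synopsis plans only descriptive summaries of safety, so a power calculation for a safety difference has no place here, and the 0.59 points per event is a unit of scale, not a forecast. The conclusion assumes that no redacted passage already requires serious events to be reported whatever their cause.

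**What to change.** Reconcile the three sections by adding one sentence to Section 6.3.1.1:

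> Neither exception applies to an event that meets a seriousness criterion in Section 6.3.1.2; such events are recorded and reported as SAEs whatever their attributed cause.

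The cost is a few more SAE reports and slightly less favourable SAE rates. It adds no visits, tests or patients.

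The sentence should not be widened to every event that stops study drug, because that would turn lack-of-efficacy withdrawals, already captured in disposition, into AEs.

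A by-arm table of symptom worsening from the diary is an optional addition to the SAP. It would use data already collected, and is worth adding only if the SAP safety section does not already contain one.
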